1.1 Study Design

This is an adaptive two-stage phase II clinical trial to assess the activity of the anti-TIM-3 antibody, MBG453, in patients with lower-risk MDS, not eligible for or progressing on frontline therapy. We will evaluate the overall response rate (ORR) using international working group criteria. Patients will receive MBG453 dosed at the recommended phase II dose of 800mg and administered on day 1 of a 28 day cycle.

In this study, we seek to test MBG453 monotherapy in patients with lower-risk MDS unresponsive to or progressive after standard initial therapy. We will include patients progressing on prior ESA therapy or those that have an EPO level > 500, as well as patients with MDS who have cytopenias that require treatment and who are not felt to be candidates for or lack other treatment options.

This is an adaptive two-stage Phase II trial. We will plan to treat patients with MBG453 on day 1 of a 28 day cycle. Patients will be treated with MBG453 dosed at 800mg every 28 days. AEs will be assessed, with particular attention paid to monitoring for immune mediated adverse events. The primary endpoint, ORR, will be assessed as the best response within the first 6 months of treatment. Patients may stay on treatment until progression. The study will assume a historical null response rate of 0.15 (e.g. based on MEDALIST) and will be powered to detect an ORR of 0.35 with MBG453.

Simon's two-stage design (Simon, 1989) will be used. The null hypothesis that the true response rate is 0.15 will be tested against a one-sided alternative. In the first stage, 10 patients will be accrued. If there are no more than 1 responses in these 10 patients, the study will be stopped. Otherwise, 12 additional patients will be accrued for a total of 22. The null hypothesis will be rejected if 6 or more responses are observed in 22 patients. This design yields a type I error rate of 0.09 and power of 0.80 when the true response rate is 0.35.

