Given the evidence of blood count responses in patients with advanced myeloid disease, and the favorable toxicity profile of MBG453 monotherapy, there is rationale to study MBG453 monotherapy for the treatment of lower-risk MDS. For those patients who are RBC transfusion dependent, they must have progressed after ESA therapy or be unlikely to respond to ESA therapy,

characterized by an EPO level >500, who are not felt to be candidates for or lack other treatment options. In addition, given early activity, there is particular interest in neutrophil and platelet responses to MBG453. These remain significant complications of MDS, with infectious and bleeding events identified as common causes of death from MDS. Therefore, patients with lower-risk MDS characterized by other cytopenias are also eligible if they require therapy, have cytopenias that can be assessed for IWG response, and are not eligible for or have progressed on other standard therapy.

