3.1 Eligibility Criteria

3.1.1 Lower risk MDS patients (IPSS-R score ≤ 3.5 at diagnosis) who have progressed or are refractory to/intolerant of prior therapy and meet one of the following categories:

- RBC transfusion dependent according to IWG criteria must either be unresponsive to prior ESA therapy or have an EPO level > 500
- Prior HMA therapy
- Patients with the following cytopenias who otherwise are felt to require treatment per the treating physician:
 - Platelets $< 50k/uL$
 - ANC < 500 cells/uL
- Patients with MDS with isolated del(5q) (“5q- syndrome”) must have progressed on or not tolerated lenalidomide
- Patients who are not felt to be candidates for or lack other standard treatment options. Patients with prior luspatercept exposure are eligible.
- Patients with dysplastic type CMML (WBC $< 13,000$ cells/uL) meeting the above criteria are eligible; responses will be assessed using MDS criteria

3.1.2 Age ≥ 18 years. Because no dosing or adverse event data are currently available on the use of MGB453 in participants < 18 years of age, children are excluded from this study, but will be eligible for future pediatric trials.

3.1.3 ECOG performance status ≤ 2 (see Appendix A).

3.1.4 Participants must have adequate organ and marrow function as defined below within 21 days of treatment:

- Total bilirubin ≤ 2 mg/dL (unless due to Gilbert’s in which case it must be < 3 mg/dL)
- AST(SGOT)/ALT(SGPT) $\leq 3 \times$ institutional ULN
- Creatinine clearance ≥ 30 mL/min/1.73 m² (by MDRD calculation)

3.1.5 Human immunodeficiency virus (HIV)-infected participants on effective anti-retroviral therapy with undetectable viral load over the prior 6 months are eligible for this trial.

3.1.6 Participants with known history or current symptoms of cardiac disease, or history of treatment with cardiotoxic agents, should have a clinical risk assessment of cardiac function using the New York Heart Association Functional Classification. To be eligible

for this trial, participants should be class 2B or better.

3.1.7 Ability to understand and the willingness to sign a written informed consent document.

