11.1. Antitumor Effect – MDS

Complete remission (CR): patients must have a bone marrow with ≤ 5% myeloblasts and with normal maturation of all cell lines. Persistent dysplasia may be noted. Blood counts over a duration of at least 4 weeks should show a hemoglobin ≥ 11 g/dL, platelets ≥ 100,000/uL, and absolute neutrophil count ≥ 1000/uL, without circulating blasts in the peripheral blood.

Partial remission (PR): over a duration of at least 4 weeks, all CR criteria (if abnormal prior to treatment) except:

1. Bone marrow blasts have decreased $\geq 50\%$ over pre-treatment levels but are still $> 5\%$, if elevated at baseline
2. Cellularity and morphology are not considered relevant

Marrow Complete Remission (mCR): over a duration of at least 4 weeks, bone marrow showing $\leq 5\%$ myeloblasts and with a decreased of $\geq 50\%$ over pre-treatment levels. If the peripheral blood counts show evidence of hematologic improvement responses, these will be noted in addition to the marrow CR.

Complete Remission with Partial Hematologic Recovery: $< 5\%$ blasts in the bone marrow and partial recovery of peripheral blood counts (platelets $> 50 \times 10^9/L$ and ANC $> 0.5 \times 10^9/L$).

Stable disease (SD): failure to achieve at least PR, but without evidence of progression for > 8 weeks.

Hematologic Responses According to the 2006 Hematologic Response Criteria:

Hematologic Improvement: HI is assessed in addition to CR/PR/mCR/SD.

1. Erythroid response: pretreatment level < 11 g/dL, showing a hemoglobin increase by ≥ 1.5 g/dL over at least 8 weeks
2. Platelet response: pretreatment level $< 100,000/uL$; showing:
 - a. Absolute increase $\geq 30,000$ if baseline $> 20,000$
 - b. Absolute increase $> 20,000$ and by at least 100% increase if baseline $< 20,000$
3. Neutrophil response: pretreatment level $< 1000/uL$, showing an absolute increase $> 500/uL$ and at least a 100% increase

Transfusion Independence: pretreatment requirement of at least 4U RBC within an 8 week period for a Hgb < 9 g/dL, no transfusions needed over an 8 week period

Hematologic Responses According to Proposed 2018 Hematologic Response Criteria:

We will also collect responses according to the proposed 2018 criteria. Patients will be categorized at baseline based on transfusion needs in the prior 16 weeks into three groups:

1. Non-transfusion Dependent (NTD): 0-2 RBCs in 16 weeks

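### Section 3.1.1 lets patients enter on prior HMA or lack of options with no baseline cytopenia, so HI and TI can be out of reach for a patient who still counts in the 6-of-22 test

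*Combined protocol and SAP*

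**What the plan says.** **Eligibility.** Section 3.1.1 takes patients with IPSS-R of 3.5 or less at diagnosis "who have progressed or are refractory to/intolerant of prior therapy and meet one of the following categories". Two of the bullets are "Prior HMA therapy" and "Patients who are not felt to be candidates for or lack other standard treatment options". Neither states a count or a transfusion need. Platelets below 50k/uL and ANC below 500/uL form a separate bullet.

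**Population described elsewhere.** Section 1.1 (Study Design) includes "patients with MDS who have cytopenias that require treatment and who are not felt to be candidates for or lack other treatment options", which joins the two conditions. Section 2.3, speaking of patients with cytopenias other than RBC transfusion dependence, makes them eligible if they need therapy and "have cytopenias that can be assessed for IWG response".

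**Endpoint.** Section 11.1 counts CR, PR, CRh, HI and TI as response, with the 2006 criteria primary. HI needs a pretreatment hemoglobin below 11 g/dL, platelets below 100,000/uL or ANC below 1000/uL. TI needs a "pretreatment requirement of at least 4U RBC within an 8 week period for a Hgb" below 9 g/dL. CRh needs marrow blasts below 5%, platelets above 50 x 10^9/L and ANC above 0.5 x 10^9/L.

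**Analysis set and test.** Section 13.7 makes every patient given at least one dose evaluable. Section 13.1 stops after 10 patients if there is no more than 1 response, and otherwise rejects the 0.15 null at 6 or more responses in 22.

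**The concern.** Section 2.3 recognises that a patient has to be assessable for response, but that condition did not reach the section against which eligibility is confirmed. The rationale in 2.3 rests on blood-count response, and HI and TI are the parts of the composite that measure it. A patient with no baseline cytopenia and no qualifying transfusion need can be scored only on CR, PR and CRh, yet is counted like any other dosed patient.

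With a cutoff of 6 in 22, one or two such patients are enough to change the operating characteristics. The direction is not fixed. Such a patient may have little chance of scoring, or may fit the CRh wording before the first dose.

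**Working it through.** **1. Does anything else require a cytopenia at entry?** No. The rest of 3.1 and all of 3.2 set no count condition. Section 3.1.4 refers to marrow function but lists only bilirubin, AST/ALT and creatinine clearance. IPSS-R is taken at diagnosis, so it does not secure a cytopenia at study entry.

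**2. Where do the sections disagree?**

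| 3.1.1 bullet | 1.1 (Study Design) | 2.3 | Result |
|---|---|---|---|
| Lack of other options | Joined to cytopenias that require treatment | For other-cytopenia patients: need for therapy and IWG assessability | Direct conflict with 1.1 |
| Prior HMA | Not mentioned | Not mentioned | Silent; no condition in any of the three |

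**3. What can the admitted patient score?** Take hemoglobin >=11 g/dL, platelets >=100,000/uL, ANC >=1000/uL and no qualifying transfusion need.
- HI: closed, because none of the three pretreatment limits is met.
- TI: closed, because the transfusion precondition is not met.
- CRh: both count limits are met at baseline. With marrow blasts below 5%, the whole CRh wording is met at baseline.
- CR: the count limits are met. The result then turns on the marrow wording ("with normal maturation of all cell lines. Persistent dysplasia may be noted"), the blast limit and the absence of circulating blasts.

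**4. Reproduce the stated design.** Inputs from 13.1: n1 = 10, stop at <=1; n = 22, reject at >=6; p0 = 0.15; p1 = 0.35.

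P(reject | p) = sum over x = 2..10 of b(x; 10, p) * P[Bin(12, p) >= 6 - x]

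- p = 0.15: 0.0907 (stated 0.09)
- p = 0.35: 0.8040 (stated 0.80)

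The stated figures reproduce.

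**5. Effect of k such patients.** The documents give no k; k = 1 and k = 2 are assumptions. Place the k patients at random over the 22 positions, so that k1 fall in stage 1 with weight C(10,k1)*C(12,k-k1)/C(22,k). The weights are 12/22 = 0.5455 and 10/22 = 0.4545 for k = 1 (k1 = 0, 1), and 0.2857, 0.5195 and 0.1948 for k = 2 (k1 = 0, 1, 2). Apply the rule in step 4 with 10 - k1 and 12 - (k - k1) ordinary patients, adding 0 or 1 response for each special patient.

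*Bound A: they never respond; the others respond at 0.35 (power).*
- k = 1: 0.5455*0.7731 + 0.4545*0.7529 = 0.764
- k = 2: 0.2857*0.7353 + 0.5195*0.7182 + 0.1948*0.6906 = 0.718

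*Bound B: they always count as responders; the others respond at 0.15 (false rejection).*
- k = 1: 0.5455*0.1702 + 0.4545*0.1919 = 0.180
- k = 2: 0.2857*0.2800 + 0.5195*0.3362 + 0.1948*0.3523 = 0.323

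| k of 22 | Power, bound A | Rejection at 0.15, bound B |
|---|---|---|
| 0 | 0.804 | 0.091 |
| 1 | 0.764 | 0.180 |
| 2 | 0.718 | 0.323 |

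Any response rate between never and always gives results between the bounds and the k = 0 row, or on the other side of it.

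**The case against.** The best case against the point has four parts.

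- **The group is close to empty.** All three counts must be above the limits, with no qualifying transfusion need, in a patient who has also progressed on, or is refractory to or intolerant of, prior therapy. Section 2.1 says lower-risk patients are generally treated for transfusion needs and cytopenias. This stands: it limits the priority, and no figure in the documents supports any particular k.
- **The list is not a pure either/or list.** The bullet saying that del(5q) patients "must have progressed on or not tolerated lenalidomide" is worded as a restriction, and the CMML bullet refers back to the other criteria. This stands for del(5q). A reader might infer that del(5q) is a third entry route without a cytopenia, but the wording fits a limit on those patients better than a way in. It does not rescue the prior-HMA and lack-of-options bullets, which contain nothing to restrict.
- **The sections mostly do not contradict each other.** A reader might infer that 1.1 and 2.3 both require an assessable cytopenia of everyone. They do not. Section 1.1 also takes patients progressing on prior ESA therapy without naming a count, and 2.3 states assessability only for patients with other cytopenias. Neither mentions prior HMA or del(5q). The direct conflict is therefore limited to lack of options.
- **These patients need not lower power.** This stands. Because they meet the CRh count limits at baseline, presenting the matter only as lost power would be wrong, and both bounds are needed.

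**Conclusion.** The point holds as a gap in the operative eligibility rule. The lack-of-options bullet conflicts with 1.1, the prior-HMA bullet has no cytopenia condition anywhere, and a patient admitted by either can be closed to HI and TI while counting among the 22.

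The size is an assumption and runs both ways. For 1 or 2 such patients, power is 0.764 or 0.718 instead of 0.804 at one extreme, and rejection at a 0.15 rate in the others is 0.180 or 0.323 instead of 0.091 at the other. Both extremes rest on an assumed k, on random placement over the two stages, and on these patients never or always scoring. The likely number is small and may be zero.

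A reader might infer that the design's type I error and power are misstated. They are not: both reproduce when every enrolled patient is assessable. The priority is minor.

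**What to change.** Reconcile 3.1.1 with 1.1 and 2.3. Add one sentence to the 3.1.1 stem: whatever the category, each patient must have at least one baseline cytopenia or transfusion need assessable under the 2006 criteria in 11.1, namely hemoglobin <11 g/dL, platelets <100,000/uL, ANC <1000/uL, or >=4 U RBC in 8 weeks for hemoglobin <9 g/dL. The platelet and ANC bullets already meet this, so in practice it affects prior HMA, lack of options, and CMML patients who enter through those bullets.

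The sponsor should also settle whether the need-for-treatment condition in 1.1 and 2.3 applies to these two categories, since the added sentence does not answer that. It also does not deal with cytopenic patients who meet the CRh limits at baseline; that belongs to the CRh definition in 11.1.

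The cost is a one-sentence amendment, checked from the screening CBC and the prior 16-week transfusion history already in the study calendar, and an occasional extra screen failure.

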3.2 Exclusion Criteria

3.2.1 Participants who have had chemotherapy or radiotherapy within 14 days or five half-lives, whichever is shorter, prior to the first dose of study treatment.

3.2.2 Participants who are receiving any other investigational agents; a washout of 14 days or 5 half-lives, whichever is longer, is required. The washout period for biologic agents should be 28 days since the last dose.

3.2.3 Prior exposure to a TIM-3 inhibitor.

3.2.4 Active autoimmune disease requiring > 10 mg per day of prednisone or the equivalent. Inactive or controlled autoimmune disease is allowed.

3.2.5 Prior solid organ transplant is exclusionary. Patients with prior hematopoietic cell transplant are eligible if they are over 6 months from transplant and not on any related immunosuppressive therapy.

3.2.6 History of allergic reactions attributed to compounds of similar chemical or biologic composition to MBG453.

3.2.7 Active untreated or concurrent malignancy that is distinct in primary site or histology, excluding:

- The following will not be exclusionary: non-melanoma skin cancer, noninvasive colonic polyps, superficial bladder tumors, cervical cancer in-situ, ductal carcinoma in situ of the breast, monoclonal B-cell lymphocytosis, or monoclonal gammopathy of undetermined significance.
- Hormonal therapy is allowed.
- History of other malignancy is allowed if not requiring active management.
- Other malignancies that were treated with curative intent at least 1 year prior to study screening and without evidence of active disease will be allowed.
- Participants with a prior or concurrent malignancy whose natural history or treatment does not have the potential to interfere with the safety or efficacy assessment of the investigational regimen are eligible for this trial pending discussion with the principal investigator.

3.2.8 Participants with uncontrolled intercurrent illness.

3.2.9 Participants must not have clinically active HBV or HCV; testing is not required

3.2.10 Receipt of a live vaccination within 28 days of cycle 1 day 1

3.2.11 Participants with psychiatric illness/social situations that would limit compliance with study requirements.

3.2.12 Female contraception is required. Pregnant women are excluded from this study because MBG453 is an agent with the potential for teratogenic or abortifacient effects. Because there is an unknown but potential risk for adverse events in nursing infants secondary to treatment of the mother with MBG453, breastfeeding should be discontinued. Women of child-bearing potential should use highly effective methods of contraception during treatment and for 150 days after the last dose of MBG453.

3.3 Inclusion of Women and Minorities

Both men and women of all races and ethnic groups are eligible for this trial.

NIH policy requires that women and members of minority groups and their subpopulations be included in all NIH-supported biomedical and behavioral research projects involving NIH-defined clinical research unless a clear and compelling rationale and justification establishes to the satisfaction of the funding Institute & Center (IC) Director that inclusion is inappropriate with respect to the health of the subjects or the purpose of the research. Exclusion under other circumstances designated by the Director, NIH, upon the recommendation of an IC Director based on a compelling rationale and justification. Cost is not an acceptable reason for exclusion except when the study would duplicate data from other sources. Women of childbearing potential should not be routinely excluded from participation in clinical research. Please see <http://grants.nih.gov/grants/funding/phs398/phs398.pdf>.

4 REGISTRATION PROCEDURES

4.1 General Guidelines for DF/HCC Institutions

Institutions will register eligible participants in the Clinical Trials Management System (CTMS) OnCore. Registrations must occur prior to the initiation of any protocol-specific therapy or intervention. Any participant not registered to the protocol before protocol-specific therapy or intervention begins will be considered ineligible and registration will be denied.

An investigator will confirm eligibility criteria and a member of the study team will complete the protocol-specific eligibility checklist.

Following registration, participants may begin protocol-specific therapy and/or intervention. Issues that would cause treatment delays should be discussed with the Overall Principal Investigator (PI). If the subject does not receive protocol therapy following registration, the subject must be taken off study in the CTMS (OnCore) with an appropriate date and reason entered.

4.2 Registration Process for DF/HCC Institutions

Applicable DF/HCC policy (REGIST-101) must be followed.

5. TREATMENT PLAN

5.1. Treatment Regimen

We will plan to treat patients with MBG453 on day 1 of a 28-day cycle. Patients will be treated with MBG453 dosed at 800mg every 28 days. AEs will be assessed, with particular attention paid to monitoring for immune mediated adverse events. The primary endpoint, ORR, will be assessed as the best response during the first 6 months of treatment. Patients may stay on treatment until progression. The study will assume a historical null response rate of 0.15 (e.g. based on MEDALIST) and will be powered to detect an ORR of 0.35 with MBG453.

MBG453 will be administered on day 1 of each cycle, where 28 consecutive days is defined as a treatment cycle. Treatment will be administered on an outpatient basis. Reported adverse events and potential risks are described in Section 7. Appropriate dose modifications are described in Section 6. No investigational or commercial agents or therapies other than those described below may be administered with the intent to treat the participant's malignancy.

Patients should not receive pre-medication to prevent infusion reactions before the first infusion of MBG453, in order to determine if pre-medication is necessary. If a patient experiences an infusion reaction he/she may receive pre-medication on subsequent dosing days. The pre-medication should be chosen per institutional standard of care, at the discretion of the treating investigator. Acute allergic reactions should be treated as per institutional standard of care. In the event of anaphylactic/anaphylactoid reactions, this includes any therapy necessary to restore normal cardiopulmonary status. If a patient experiences a Grade 3 anaphylactic/anaphylactoid reaction, the patient will be discontinued from the study. Patients should be treated at a facility equipped for cardiopulmonary resuscitation. Appropriate resuscitation equipment should be available at the bedside and a physician readily available.

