5.6. Criteria for Taking a Participant Off Protocol Therapy

Duration of therapy will depend on individual response, evidence of disease progression and tolerance. In the absence of treatment delays due to adverse event(s), treatment may continue for until one of the following criteria applies:

- Disease progression
- Intercurrent illness that prevents further administration of treatment
- Unacceptable treatment-related adverse event(s)
- Participant demonstrates an inability or unwillingness to comply with the medication regimen and/or study requirements
- Participant and/or treating investigator decides to withdraw from the protocol therapy
- General or specific changes in the participant's condition render the participant unacceptable for further treatment in the judgment of the treating investigator

Participants will be removed from the protocol therapy when any of these criteria apply. The reason for removal from protocol therapy, and the date the participant was removed, must be documented in the case report form (CRF). Alternative care options will be discussed with the participant. If MBG453 becomes commercially available and reimbursable, patients may choose to transition off protocol therapy to commercial product.

In the event of unusual or life-threatening complications, treating investigators should immediately notify the Overall PI, [name] at [contact] or paged at [contact].

When a participant is removed from protocol therapy and/or is off of the study, the participant's status must be updated in OnCore in accordance with [REGIST-OP-1](#).

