5.7. Duration of Follow Up

Participants will be followed for 12 months after removal from protocol therapy (30, 150, 250 days, and at 12 months, ± 7 -day window) or until death, whichever occurs first. Follow-up will assess for survival and progression and may be done in person or via phone/electronically. If three consecutive follow-ups are missed the patient will be considered lost to follow up and censored at the last verified date of clinical follow up (in person or electronically verified). Participants removed from protocol therapy for unacceptable adverse event(s) will be followed until resolution or stabilization of the adverse event.

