5.8. Criteria for Taking a Participant Off Study

Participants will be removed from study when any of the following criteria apply:

- Lost to follow-up
- Withdrawal of consent for data submission
- Death

The reason for taking a participant off study, and the date the participant was removed, must be documented in the case report form (CRF). In addition, the study team will ensure the participant's status is updated in OnCore in accordance with [REGIST-OP-1](#).

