6. DOSING DELAYS/DOSE MODIFICATIONS

MBG453 may be delayed due to toxicities. Doses may be delayed for up to 28 days for toxicity; toxicities that result in more than 28 days delay should result in discontinuation from the study medication. Patients that are deriving clinical benefit but require a treatment delay beyond 28 days for non-toxicity events should be discussed with the principal investigator.

Dosing may be resumed once an AE has resolved to baseline or to Grade 1. If a treating investigator considers it in the patient's best interest to resume therapy before resolution of an AE or to resume without dose modification this may be considered on a case-by-case basis after discussion with the overall PI of the trial.

Dose modifications of MBG453 may be accomplished through dose reduction or altering the treatment interval; provisional dose levels are shown below.

Dose delays and modifications will be made as indicated in the following table(s). The descriptions and grading scales found in the revised NCI Common Terminology Criteria for Adverse Events (CTCAE) version 5.0 will be utilized for dose delays and dose modifications. A copy of the CTCAE version 5.0 can be downloaded from the CTEP website

http://ctep.cancer.gov/protocolDevelopment/electronic_applications/ctc.htm.

Dose Level	Dose
-2	240 mg every 28 days
-1	400 mg every 28 days
0	800 mg every 28 days

If the patient experiences an AE meeting the criteria for DLT as outlined in section 5.4, including events outside the DLT period, treatment should be held. Patients may resume treatment after resolution to Grade 1 or to the patient's baseline value. If this event occurs during the first cycle (whether or not they are among the first 6 patients being evaluated for DLT assessment) a dose modification must be made. If this event occurs after the first cycle the patient may resume at the same or a lower dose at the discretion of the investigator. Specific guidance is provided below.

Infusion Reaction	Management/Next Dose for MBG453
≤ Grade 1	Decrease infusion rate until recovery
Grade 2	Stop Infusion. Before restarting, pre-medicate according to local institutional guidelines. Restart infusion at 50% of previous rate under continuous observation. Ensure that there is a minimum observation period of 1 hour prior to restarting the infusion(s). If the AE recurs at the reinitiated slow rate of infusion, and despite oral pre-medication, then discontinue treatment
Grade 3	Discontinue treatment

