7.3.4. Serious Adverse Events

Definitions

A serious adverse event (SAE) is defined as one of the following:

- Is fatal or life-threatening
- Results in persistent or significant disability/incapacity
- Constitutes a congenital anomaly/birth defect
- Is medically significant, i.e., defined as an event that jeopardizes the patient or may require medical or surgical intervention to prevent one of the outcomes listed above
- Requires inpatient hospitalization or prolongation of existing hospitalization,
 - Note that hospitalizations for the following reasons should not be reported as serious adverse events:
 - Routine treatment or monitoring of the studied indication, not associated with any deterioration in condition
 - Elective or pre-planned treatment for a pre-existing condition that is unrelated to the indication under study and has not worsened since signing the informed consent
 - Social reasons and respite care in the absence of any deterioration in the patient's general condition

Note that treatment on an emergency outpatient basis that does not result in hospital admission and involves an event not fulfilling any of the definitions of a SAE given above is not a serious adverse event. Please also see below for reporting exclusions.

All patients must be followed for safety for 150 days after the last dose of MBG453.

After the 30-Day on-site safety follow-up visit, patients may be followed via telephone call (or onsite visit if patient happens to be visiting the site) up to 150 days after the last dose of MBG453.

Adverse events separate from the progression of malignancy (i.e. deep vein thrombosis at the time of progression or hemoptysis concurrent with finding of disease progression) will be reported as per usual guidelines used for such events with proper attribution regarding relatedness to the drug.

Any SAE experienced after 150 days of the last dose of MBG453 will only be reported to Novartis Safety if the investigator suspects a relationship to the study treatment.

Progression of malignancy (including fatal outcome), if documented by use of an appropriate method (for example per IWG guidelines (Cheson et al 2006)), should not be reported as an SAE except if the investigator considers the progression of malignancy is related to the study treatment.

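### Section 5.1 takes a patient with a Grade 3 anaphylactic reaction off the study, which conflicts with the off-therapy, off-study and follow-up rules in Sections 5.6 to 5.8, 6 and 7.3.4

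*Combined protocol and SAP*

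**What the plan says.** Section 5.1 (Treatment Regimen) states: "If a patient experiences a Grade 3 anaphylactic/anaphylactoid reaction, the patient will be discontinued from the study".

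Other sections treat the same situation differently:

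- **Section 6, infusion-reaction table.** The entry for Grade 3, and again for Grade 4, is "discontinue treatment". Nothing is said about leaving the study. For long delays the same section says that "toxicities that result in more than 28 days delay should result in discontinuation from the study medication".
- **Section 5.6.** An unacceptable treatment-related adverse event is listed as a reason to come off protocol therapy.
- **Section 5.7.** "Participants will be followed for 12 months after removal from protocol therapy", with contacts at 30, 150 and 250 days and at 12 months, unless death comes first. It adds: "Participants removed from protocol therapy for unacceptable adverse event(s) will be followed until resolution or stabilization of the adverse event".
- **Section 5.8.** "Participants will be removed from study when any of the following criteria apply". Three criteria follow: loss to follow-up, withdrawn consent to data submission, and death.
- **Section 7.3.4.** "All patients must be followed for safety for 150 days after the last dose of MBG453". Footnote i of the study calendar (Section 10) repeats the 150 days as mandatory.

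**The concern.** The protocol treats leaving therapy and leaving the study as two separate statuses. Each has its own section (5.6 and 5.8), its own date and reason on the case report form, and its own status update in the registration system. The 5.1 sentence uses the off-study term for an event that every other relevant section handles as an off-therapy event. A site that took 5.1 at its word could record an off-study date.

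At stake is the follow-up after the reaction: the course of the event itself, the 150-day safety window, and the survival and progression contacts. These feed the secondary endpoints in Section 13.1 (adverse events, 1-year OS, PFS, time to progression). Section 13.6 estimates OS and PFS by Kaplan-Meier, which assumes that censoring is unrelated to prognosis. That assumption is hard to defend for a patient withdrawn because of a severe drug reaction.

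**Working it through.** The plan states no figure on this point, so the main check is a comparison of texts. The size is then bracketed under stated assumptions.

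**1. What each section does with the patient**

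| Section | Treatment | Study status or follow-up |
|---|---|---|
| 5.1 (Grade 3 anaphylaxis) | not stated separately | off the study |
| 6, infusion table (Grades 3 and 4) | stops | not mentioned |
| 5.6 (unacceptable related event) | off protocol therapy | not off study |
| 5.7 | already off therapy | event to resolution or stabilization; 12 months of contacts |
| 5.8 | not addressed | three off-study reasons, no adverse event |
| 7.3.4 and calendar footnote i | last dose given | 150 days of safety follow-up |

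Sections 5.1 and 6 agree that dosing ends at Grade 3. They differ on whether the patient remains under observation. Sections 5.7 and 7.3.4 cannot be carried out for a patient who has left the study. There is also an anomaly by grade: 5.1 names Grade 3 only, so on a literal reading a Grade 3 patient leaves the study while a Grade 4 patient, covered only by Section 6, stops treatment and keeps full follow-up. That pattern suggests a drafting slip.

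**2. What would and would not be lost for one such patient**

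- Lost on a literal reading: follow-up of the event to resolution or stabilization, the 150-day safety period, and up to four scheduled survival and progression contacts.
- Kept: the report of the reaction. Sections 7.3.2 and 7.6 require adverse events after the first dose to be reported, and 13.7.1 makes participants evaluable for toxicity from that dose.
- Kept: the place in the ORR denominator. Section 13.7 counts every patient with at least one dose.
- Unchanged: the Simon design. Exact binomial sums for the stated rule (stop at 1 or fewer of 10; reject at 6 or more of 22) give type I error 0.0907 and power 0.804, against the stated 0.09 and 0.80.

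**3. How often the sentence might apply**

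The documents give no rate of Grade 3 anaphylaxis, so the per-patient rate q is an assumption. With the maximum of 22 patients (Section 13.2), P(at least one) = 1 − (1 − q)^22:

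- q = 0.25%: 5.3%; expected number 0.05
- q = 1%: 1 − 0.99^22 = 19.8%; expected number 0.22
- q = 2%: 1 − 0.98^22 = 35.9%; expected number 0.44

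The lowest value is 1/404. The numerator is the single serious suspected infusion reaction in Section 7.1.5, and the denominator is 252 + 152 patients treated as of July 2019 (Section 2.2). It is only a proxy: that case was shaking chills, with no grade given and no mention of anaphylaxis.

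**4. Effect on precision if one patient is lost**

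Take an assumed 1-year OS of 0.80 and a normal approximation, with half-width 1.96 × √(0.80 × 0.20 / n). For n = 22 this is 0.167; for n = 21 it is 0.171.

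**The case against.** The strongest reply is that the rest of the protocol already settles the matter. Section 5.1 concerns the regimen and itself sends the reader to Section 6 for dose modifications. Section 6 stops treatment only, 5.7 prescribes follow-up after exactly this kind of removal, and 7.3.4 is unconditional. Data are lost only if a site follows one loose sentence against all of these. That is fair, and it is why the point is minor. It does not remove the conflict, because the 5.1 sentence is operative and specific to the event.

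One could also say that 5.1 simply adds a reason to 5.8, whose list is not labelled exhaustive; Section 4.1, for instance, takes registered patients who never receive therapy off study. But those patients have no dose to follow up. A dosed patient falls under 7.3.4, so that conflict would remain.

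A reader might infer that the toxicity case would vanish from the safety data, or that the response rate would be affected. The documents do not support either: reporting of the reaction and the ORR denominator are both secured elsewhere. Nor should the 5% be read as an estimate from prior experience, since the case behind it is not described as the triggering event.

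**Conclusion.** The inconsistency is real and minor. Followed literally, 5.1 would end required safety, survival and progression follow-up after a severe drug reaction, and could censor OS and PFS informatively. The censoring is an inference: the plan states a censoring rule only for patients lost to follow-up (5.7), and an off-study date would ordinarily be handled the same way.

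The numerical effect is small. At most a few patients are likely to be involved, with a probability of about 5% to 36% of at least one in 22 under assumed rates of 0.25% to 2%. Losing one patient (1/22 = 4.5% of the sample) widens the OS interval only slightly under the assumed 0.80. OS and PFS are estimated without a stated hypothesis test. The case for acting rests on the contradiction with a mandatory follow-up duty, and frequency adds little to it.

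**What to change.** Reconcile the 5.1 sentence with Sections 5.6 to 5.8, the Section 6 infusion-reaction table and Section 7.3.4. Use the protocol's own distinction between leaving protocol therapy and leaving the study, so that the 5.7 follow-up and the 150-day safety period still apply to these patients. Whether and when treatment stops is for the sponsor to confirm; this point takes no position on it.

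The cost is a few words in 5.1. No visit or assessment is added beyond those already required, and the sample size, the Simon boundaries and the analysis sets stay as they are.
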